11.4.4 Analyses of pharmacokinetic and pharmacodynamics variables

Pharmacokinetic (PK) analyses will be performed using the PK population via pooling all available data.

Serum trough concentrations of functional sarilumab will be summarized using descriptive statistics (including number, arithmetic and geometric means, standard deviation, standard error of the mean (SEM), CV, minimum, median, and maximum) by dose, overall and by weight group, for each visit. The samples will be considered non eligible for these analyses if the previous dosing time is <11 days or >17 days before the sampling time for q2w regimens; <5 days or >9 days before the sampling time for qw regimens. Concentrations below the lower limit of quantification (LLOQ) will be set to zero for samples at predose (Week 0). Other concentrations below LLOQ will be replaced by LLOQ/2. Semi log plots of concentration over time will also be provided (no value at time 0). Serum concentrations of functional sarilumab will be summarized using descriptive statistics mentioned above by immunogenicity status for each dose at each visit (see [Section 9.1](#) and [Section 9.7](#)).

A PopPK model will be developed using [REDACTED] to describe the PK profile of sarilumab. A PopPK model will be used to estimate population and individual PK parameters, the sources of PK variability and assess the influence of covariates on PK parameters. The potential covariates to be evaluated in the PopPK analysis include [REDACTED]

[REDACTED] The predicted individual sarilumab PK exposure (C_{max} and $AUC_{0-\tau}$) following the first dose will be summarized using descriptive statistics by dose and weight group. PopPK results may be presented in a separate document from the CSR.

Serum concentrations of IL-6, total sIL-6R α and hs-CRP will be summarized using descriptive statistics (including number, arithmetic and geometric means, standard deviation, standard error of the mean [SEM], CV, minimum, median, and maximum) by dose and weight group for each visit ([Section 9.1](#) and [Section 9.7](#)).

[REDACTED]

[REDACTED]

[REDACTED]

[REDACTED]

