After completing the investigation of the ascending dose regimen cohorts in the dose-finding portion of the 12-week core treatment phase, one dose regimen will be selected by the Dose Escalation Committee (DEC) and additional patients will be enrolled at the selected dose regimen (second portion of the core treatment phase) to obtain 18 evaluable patients per weight group with that selected dose regimen in order to provide sufficient precision for PK parameters and PK-PD relationship assessments. Those patients will undergo the same assessments as patients recruited in the dose-finding portion.

Additionally, after completing the enrollment of dose-finding and second portions, a third portion where approximately 28 additional patients will be enrolled directly to the selected dose regimen to achieve a total of approximately 100 treated patients for the entire study as per a health authority recommendation. These patients will undergo the same on-site visits during the 12-week core treatment phase as patients recruited in the dose-finding and second portions; however, the patients in the third portion will not have the sarilumab PK sampling visits between Baseline and Week 2.

An additional treatment period in the extension phase will allow collection of long-term safety and clinical response data for sarilumab in pcJIA patients. This extension phase is up to 144 weeks for patients enrolled in the dose-finding and second portions and up to 84 weeks for patients enrolled in the third portion. Patients enrolled in the dose-finding portion who are already in the extension phase at time of dose regimen selection and who did not receive the selected dose regimen will have their dose regimen adjusted to the selected dose.

To minimize the amount of blood collected, Group B patient (<30 kg and \geq 10 kg) in the dose-finding and second portions will be randomized to 1 of 2 different sarilumab PK sample collection schedules. The PK analyses will integrate these sampling schedules to describe the PK profile of sarilumab (see [Section 9.1](#)). No PK sample collection is planned between Baseline and Week 2 for patients enrolled in the third portion. Total volume of blood withdraw for the study will not exceed 3% of the total blood volume during a period of 4 weeks and not exceed 1% of the total blood volume at any single time (16).

Furthermore, the planned frequent assessments control risk to study participants.

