11.3.3 Pharmacokinetic, pharmacodynamics, and immunogenicity population

The PK population will consist of all patients in the safety population with at least one post-dose, nonmissing serum concentration value. The PD population will consist of all patients in the safety population with at least one post-dose biomarker assessment. The ADA population will consist of all patients in the safety population with at least one post-dose, evaluable ADA sample. Patients will be analyzed according to the treatment actually received.

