### 2.3.1 Pharmacokinetic, pharmacodynamics and immunogenicity population

The PK population will consist of all patients in the safety population with at least one post-dose, non-missing serum concentration value.

The PD population will consist of all patients in the safety population with at least one post-dose biomarker assessment.

The ADA population will consist of all patients in the safety population with at least one post-dose, evaluable ADA sample.

In all cases, patients will be analyzed according to the treatment actually received.

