#### **2.4.4 Analyses of pharmacokinetic variables**

Serum trough concentrations of functional sarilumab will be summarized using descriptive statistics (including number, arithmetic and geometric means, SD, standard error of the mean (SEM), CV (%), minimum, median, and maximum) by dose regimen cohort, overall and by weight group, for each visit. The samples will be considered non-eligible for these analyses if the previous dosing time is <11 days or >17 days before the sampling time for every other week regimens; <5 days or >9 days before the sampling time for every week regimens. Concentrations below the lower limit of quantification (LLOQ) will be set to zero for samples at predose (Week 0). Other concentrations below LLOQ will be replaced by LLOQ/2. Semi-log plots of concentration over time will also be provided (no value at time 0). Serum concentrations of

functional sarilumab will be summarized using the descriptive statistics mentioned above by immunogenicity status for each dose regimen cohort at each visit.

Listings of serum concentration will be provided for each individual patient including subject identification (ID), gender, age, first dose date, visit number, categorized time point (0 for trough level and 1 for pre-dose), date/time of previous dose, PK sampling date/time, duration since first dose (days), duration since previous dose (dd:hh), and serum concentration (mg/L).

All PK analyses will be performed using the PK population.

[REDACTED]

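### As visible, the first-dose Cmax and AUC0-tau summary pools third-portion patients who have no sample before the Week 2 trough, so the spread it shows is likely too small

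*Protocol*

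**What the plan says.** **Analysis set.** Protocol 11.4.4: "Pharmacokinetic (PK) analyses will be performed using the PK population via pooling all available data". Protocol 11.3.3: "The PK population will consist of all patients in the safety population with at least one post-dose, nonmissing serum concentration value". SAP 2.3.1 sets the same threshold ("at least one post-dose, non-missing serum concentration value"), and SAP 2.4.4 adds "All PK analyses will be performed using the PK population".

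**The table.** Under Protocol 9.1.4 and 11.4.4 the exposure measures come from the PopPK model. Predicted individual Cmax and AUC0-tau "following the first dose will be summarized using descriptive statistics by dose and weight group". Portion is not a grouping factor.

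**Sampling.** Protocol 4.3.2: "No PK sample collection is planned between Baseline and Week 2 for patients enrolled in the third portion". Protocol 9.1.1 drops Visits 3 to 6 for these patients. In the first two portions, Group A has four post-dose samples before Week 2 (Days 3, 5, 8 and 12) and each Group B schedule has two.

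**Restriction by portion.** The only visible one is for the second interim analysis (Protocol 11.5, SAP 3).

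**Hidden or separate material.** Text beside the first-dose sentence in 11.4.4 and at the end of SAP 2.4.4 is redacted, and Protocol 11.4.4 allows that "PopPK results may be presented in a separate document from the CSR".

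**The concern.** First-dose Cmax and AUC0-tau are two of the three measures in the primary endpoint (Protocol 9.1, SAP 2.1.3). An individual prediction from a population model is a compromise between the patient's own samples and the value the model expects for that patient's covariates. The less the samples say about a quantity, the closer the prediction lies to the expected value.

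Third-portion patients are dosed every two weeks (Protocol 1.2.2.3), so their Week 2 pre-dose sample is the trough at the end of the first interval. Later troughs inform clearance but say little about absorption or the peak. Mixing these predictions with those from patients sampled within the interval narrows the displayed spread. A reader of the final table could take that for low between-patient variability when part of it only reflects sparser sampling.

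**Working it through.** **1. Cell sizes (from the documents)**

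- Third portion: about 28 patients, each weight group capped at 70% (Protocol 8.4). 0.70 x 28 = 19.6, rounded to 20; 28 - 20 = 8. This reproduces the stated 20 versus 8.
- Selected regimen, first two portions: 6 + 12 = 18 evaluable per weight group (Protocol 6.1).
- PK-population entry does not require evaluability. The synopsis plans about 72 enrolled for 60 evaluable; if that ratio applies here, 18 x 72/60 = 21.6, about 22 per group.

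**2. Third-portion share, f = k/(base + k)**

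| k added | base 18 | base 21.6 |
|---|---|---|
| 8 | 8/26 = 30.8% | 8/29.6 = 27.0% |
| 20 | 20/38 = 52.6% | 20/41.6 = 48.1% |

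The range is 27-53%. If one group has 20, the other has 8, so the upper end can occur in one group only.

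**3. Effect on the displayed SD**

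Let r12 and r3 be SD(log predicted)/SD(log true) for the first two portions and the third portion, and q = r3/r12. With equal means and equal true spread,

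pooled SD / SD in portions 1-2 = sqrt(1 - f(1 - q^2)).

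The documents give no PK parameters, so r12 and r3 come from simulated empirical-Bayes estimates under an assumed linear one-compartment SC model with two-weekly dosing and core-phase samples only (third portion: Weeks 2, 4, 8 and 12).

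Example (Group A, Cmax; ka 0.3 and ke 0.10 per day, residual SD 0.25): shrinkage was 6.9% with full sampling and 69.8% in the third portion. So r12 = 0.931, r3 = 0.302 and q = 0.324.

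- f = 27.0%: sqrt(1 - 0.270 x 0.895) = 0.87
- f = 52.6%: sqrt(1 - 0.526 x 0.895) = 0.73

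Mildest scenario (ka 0.2, ke 0.06, residual SD 0.20): shrinkage 2.7% and 33.2%, q = 0.687, giving 0.93 and 0.85 at the same shares.

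Across all four scenarios, both weight groups and all shares in step 2, the ratio is 0.71-0.93 for Cmax and 0.77-0.93 for AUC0-tau.

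**4. Later samples and weight**

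A second simulation used 16 other assumed parameter sets, base 18 and k = 8 to 20:

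| Data | Cmax | AUC0-tau |
|---|---|---|
| Core only, or third interim (Weeks 24 and 48 added) | 0.70-0.94 | 0.77-0.95 |
| Final, no usable end-of-study (EOS) sample | 0.70-0.94 | 0.77-0.95 |
| Final, EOS quantifiable in all patients | 0.81-0.98 | 0.89-0.98 |
| Third interim, weight effect SD 0.2 on CL and V | 0.78-0.94 | 0.84-0.95 |

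Whether the EOS sample helps depends on quantifiability. It is taken 42 days after the end-of-treatment sample, so its level is exp(-42 ke) of that trough: 8%, 1.5% or 0.02% for ke = 0.06, 0.1 or 0.2 per day.

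**5. Group B**

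The two Group B schedules are themselves sparse (4-19% shrinkage for Cmax, 2-15% for AUC0-tau in the four scenarios of step 3), so some shrinkage remains in that group whatever is done about the third portion.

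**The case against.** **Redaction.** The relevant limit or a shrinkage report may sit in the hidden lines of 11.4.4 or SAP 2.4.4, or in the separate PopPK document. That stands, and it is why the point is limited to visible text. It does not remove the point: the visible wording states a pooling rule, and following it produces the effect. The pooling sentence may partly refer to model building, but the table sentence carries no restriction of its own.

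**The second interim already gives a clean table.** That analysis is limited to the first two portions, so an unmixed first-dose table could exist. It would not correct the pooled tables produced later.

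**PK precision was planned on the first two portions.** Protocol 4.3.2 ties the 18 per group to PK precision and the third portion to reaching about 100 treated patients. This is true, and it supports showing those portions on their own.

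**Small against sampling noise.** With n = 18 the 95% normal-theory interval for an SD runs from sqrt(17/30.19) = 0.75 to sqrt(17/7.56) = 1.50 times the estimate, so many of the ratios above lie within it. This stands as a limit on importance. Still, the noise can go either way, whereas this effect pushes the spread down. A true difference in mean exposure between portions would raise the pooled SD and offset part of it.

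**Stronger readings.** A reader might infer that the dose was chosen on understated variability, or that the primary PK analysis is invalid. The documents do not support either. The dose is selected from dose-finding data before the third portion enrols (Protocol 6.1.2.4, 4.3.2), and the model is separately "used to estimate population and individual PK parameters, the sources of PK variability", which does not depend on the spread of individual predictions.

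**Conclusion.** The point holds in a limited form. As visible, the plan mixes richly and sparsely sampled patients in one first-dose exposure table, and the displayed spread is likely too small. It concerns the selected-regimen rows only, at the third interim and final analyses only, and the SD, CV and possibly range only, if these are reported.

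The share of 27-53% follows from the documents, given 18 evaluable or about 22 enrolled patients per group. The direction follows from how individual model predictions behave. The size, a pooled SD about 0.7-0.95 of that in the first two portions alone, rests entirely on assumed PK values and moves toward 1 when weight explains part of the spread or the EOS sample is quantifiable.

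Dose selection, the second interim analysis, Ctrough and the model-estimated variability are untouched, and Protocol 11.4.2.3 plans no hypothesis test. Nor can one conclude that shrinkage goes unchecked: that may be covered in text that is not visible. This is a cheap reporting improvement, with medium confidence.

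**What to change.** In Protocol 11.4.4, and in SAP 2.4.4 or the PopPK plan, add wording to this effect:

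> Model-predicted individual Cmax and AUC0-tau after the first dose are tabulated for the dose-finding and second portions combined, and separately for the third portion, within each dose regimen and weight group. Shrinkage is reported for each table. Third-portion concentrations remain in the Ctrough summaries and in model fitting.

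If the redacted text or the separate PopPK document already provides this, a cross-reference is enough.

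**Cost:** a portion flag and a few sentences; no new data and no change to conduct. The downside is fewer patients per row (about 18 evaluable instead of 26-38 in a selected-regimen cell) and a wider reported spread.

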STUDY DESIGN	
Design:
 
Multicenter, open-label, two-phase study in pcJIA patients from 2 to 17 years (or country specified age requirement) of age: The two phases are:
 
1) A 12-week core treatment phase, split into 3 portions:
 
 A first sequential, ascending dose-cohort, dose-finding portion (hereafter referred to as "dose-finding portion") in which up to 3 dose regimens will be investigated in two weight groups (Group A, patients ≥ 30 kg and ≤ 60 kg and Group B, patients < 30 kg and ≥ 10 kg) in 6 evaluable patients per dose regimen weight group (around 36 patients in total). Patient enrollment will be staggered by weight group and dose regimen, starting with Group A and Dose Regimen 1 Cohort. A subsequent portion (hereafter referred to as "second portion") where approximately 24 additional patients (12 in each weight group: patients ≥ 30 kg [Group A] and patients < 30 kg and ≥ 10 kg [Group B]) will be enrolled directly to the selected dose regimen (identified based on the aggregate data from patients enrolled in the dose-finding portion) to achieve a total of 18 evaluable patients per weight group at this selected dose regimen. These patients will undergo the same 12-week core treatment phase assessments as patients recruited during the dose-finding portion. A third portion (hereafter referred to as "third portion") where approximately 28 additional patients (a cap of 70% of each weight group: patients ≥ 30 kg [Group A] and patients < 30 kg and ≥ 10 kg [Group B]) will be enrolled directly to the selected dose regimen to achieve a total of approximately 100 treated patients for the entire study. These patients will undergo the same on-site visits during the 12-week core treatment phase as patients recruited in the dose-finding and second portions; however, the patients in the third portion will not have the sarilumab PK sampling visits between Baseline and Week 2. 
The 12-week core treatment phase is from Visit 2 (baseline-Week 0) to the time that Visit 12 investigational medicinal product (IMP) is administered.

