7.2.1 Exclusion criteria related to study methodology

- E 01. Body weight < 10 kg or > 60 kg for patients enrolled in the 3 ascending dose regimen cohorts, then body weight < 10 kg for patients subsequently enrolled at the selected dose regimen cohorts
- E 02. Wheelchair-bound or bed-ridden
- E 03. Diagnosis of JIA subtypes except polyarticular RF-positive (RF+) or RF-negative (RF-) JIA or extended oJIA
- E 04. If non-steroidal anti-inflammatory drugs (NSAIDs) (including cyclo-oxygenase-2 inhibitors [COX-2]) taken, dose stable for less than 2 weeks prior to the Baseline visit and/or dosing prescribed outside of approved label
- E 05. If nonbiologic DMARD taken, dose stable for less than 6 weeks prior to the Baseline visit or at a dose exceeding the recommended dose as per local labeling

- E 06. If oral glucocorticoid taken, dose stable for <2 weeks or dose exceeding equivalent prednisone dose 0.5 mg/kg/day (or 30 mg/day) within 2 weeks prior to Baseline
- E 07. Use of parenteral or intra-articular glucocorticoid injection within 4 weeks prior to Baseline
- E 08. Prior treatment with anti-IL-6 or IL-6R antagonist therapies, including but not limited to tocilizumab or sarilumab
- E 09. Treatment with any biologic treatment for pcJIA within 5 half-lives prior to the first dose of sarilumab as follows (the required off-treatment periods and procedures may vary according to local requirements):
- Etanercept: within 4 weeks
 - Infliximab: within 8 weeks
 - Adalimumab: within 15 weeks
 - Anakinra: within 2 days
 - Canakinumab: within 19 weeks
 - Abatacept: within 10 weeks
 - Rituximab or other cell-depleting agent: within 16 weeks or until total lymphocyte count and CD 19+ lymphocyte count are normalized, whichever is longer
 - Intravenous Ig: within 15 weeks
- E 10. Treatment with a Janus kinase (JAK) inhibitor within 4 weeks prior to the first dose of sarilumab; and treatment with growth hormone within 4 weeks prior to the first dose of sarilumab (the required off-treatment periods and procedures may vary according to local requirements)
- E 11. Treatment with any investigational biologic or non-biologic product ([Appendix J](#)) within 8 weeks or 5 half-lives prior to Baseline, whichever is longer
- E 12. Lipid lowering drug stable for less than 6 weeks prior to Screening
- E 13. Exclusion related to tuberculosis:
- Active TB or a history of incompletely treated TB

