8.4 METHOD OF ASSIGNING PATIENTS TO TREATMENT GROUP

The list of randomized treatment kit numbers will be generated centrally by Sanofi. The IMPs are packaged in accordance with this list. Patients will be assigned a treatment kit by an interactive voice response system (IVRS) or an interactive web response system (IWRS).

Patients who meet the entry criteria will be included and will be dispensed the treatment kits within 2 weight groups (Group A: ≥ 30 kg and ≤ 60 kg for patients enrolled during the dose-finding portion and ≥ 30 kg for patients enrolled during the second and the third portions; Group B: < 30 kg and ≥ 10 kg for all 3 portions).

- For the dose-finding and second portions, the planned ratio of enrollments for the 2 weight groups is 1:1.
- For the third portion, there is no pre-specified enrollment ratio for the 2 weight groups, but each weight group will be capped at 70% (ie, 20 patients). As a result, the most unbalanced enrollments by weight group possible would be 20 versus 8 patients in the third portion.

Patients who meet exclusion criteria may be rescreened once during the open screening period of the study. A different patient identification will be issued. There is no requirement for a waiting period between the screen failure and the rescreening. The IVRS/IWRS report will flag rescreened patients. Patients that are rescreened will be required to sign a new consent form (if the patient has reached the legal age) or by parents or legal guardians. Visit 1 procedures must be repeated (except chest X-ray).

At the Screening Visit 1 (Day-28 to D-1, up to 31 days), the site staff will contact the IVRS/IWRS to obtain a patient number for each patient who gives informed consent. Each patient will be allocated a patient number associated with the center and allocated in chronological order in each site.

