Appendix B Volume to be administered at each injection according to body weight

Notes:

1) Volume to be administered at each injection during 12-week core treatment phase will be calculated based on Baseline (Visit 2) body weight and will be maintained during all 12-week core treatment phase.

2) Volume to be administered during the extension treatment phase will be adjustable by body weight measured at each visit in case of weight increase and if the calculation shows a need for dose increase.

3) If the selected dose regimen is one from the 3 predefined dose regimens, the patients subsequently enrolled at or changed to the selected dose regimen will use the corresponding dose in the tables below.

4) If the selected dose regimen is an intermediate dose, corresponding tables will be provided to the Investigators.

B.1 Patient in high weight group (Group A): Patients ≥ 30 kg and ≤ 60 kg for dose-finding portion and ≥ 30 kg for additional patients in the second portion

- Dose Regimen 1 and 3 Cohorts

Dose Regimen 1 Cohort (2 mg/kg q2w) and Dose Regimen 3 Cohort (2 mg/kg qw)		
Body weight (kg)	Volume per injection (mL)	Corresponding dose (mg)
≥ 30 and < 33	0.35	61.25
≥ 33 and < 37.5	0.40	70
≥ 37.5 and < 42	0.45	78.75
≥ 42 and < 46.5	0.50	87.5
≥ 46.5 and < 50.5	0.55	96.25
≥ 50.5 and < 55	0.60	105
≥ 55 and < 59.5	0.65	113.75
≥ 59.5 and < 64	0.70	122.5
≥ 64 and < 68	0.75	131.25
≥ 68 and < 72.5	0.80	140
≥ 72.5	0.85 (cap injection volume)	148.75 (cap under 150 mg)

- Dose Regimen 2 Cohort

Dose Regimen 2 Cohort (3 mg/kg q2w)		
Body weight (kg)	Volume per injection (mL)	Corresponding dose (mg)
≥30 and <31	0.50	87.5
≥31 and <34	0.55	96.25
≥34 and <37	0.60	105
≥37 and <39.5	0.65	113.75
≥39.5 and <42.5	0.70	122.5
≥42.5 and <45	0.75	131.25
≥45 and <48.5	0.80	140
≥48.5 and <51.5	0.85	148.75
≥51.5 and <54.5	0.90	157.5
≥54.5 and <57	0.95	166.25
≥57 and <63	1.00	175
≥63	1.1 (cap injection volume)	192.5 (cap under 200 mg)

B.2 Patient in low weight group (Group B): <30 kg and ≥10 kg

- Dose Regimens 1 and 3 Cohorts

Dose Regimen 1 Cohort (2.5 mg/kg q2w) and Dose Regimen 3 Cohort (2.5 mg/kg qw)		
Body weight (kg)	Volume per injection (mL)	Corresponding dose (mg)
≥10 and <12.5	0.15	26.25
≥12.5 and <16	0.20	35
≥16 and <19.5	0.25	43.75
≥19.5 and <23	0.30	52.5
≥23 and <26.5	0.35	61.25
≥26.5 and <30	0.40	70
For patients who grow over 30 kg, the following injection volume will be followed		
≥30 and <37.5	0.40	70
≥37.5 and <42	0.45	78.75
≥42 and <46.5	0.50	87.5

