## 2.4.6 Analyses of efficacy endpoints

Efficacy is considered as secondary in these studies, and will be summarized descriptively for each study (ie, disease type) separately.

Efficacy analyses will be done by dose regimen cohort and by weight group. Summaries on the non-selected doses will only include the data collected prior to the first dose adjustment to the selected dose. Data after the dose adjustment will be summarized separately ([Section 2.4.11](#)).

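### After regimen selection, only the selected regimen's Group A column can hold patients above 60 kg or on a capped dose, and the core-phase PK, PD and ACR tables do not show them separately

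*Protocol*

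**What the plan says.** Protocol 8.4 limits Group A to 30-60 kg in the dose-finding portion and sets it at or above 30 "kg for patients enrolled during the second and the third portions". Exclusion criterion E 01 (Protocol 7.2.1) matches this: the upper limit of 60 kg applies to the three ascending cohorts, "then body weight < 10 kg for patients subsequently enrolled at the selected dose regimen cohorts". The second and third portions enrol only to the selected regimen. The second runs "to achieve a total of 18 evaluable patients per weight group at this selected dose regimen"; for the third, Protocol 8.4 states that "the most unbalanced enrollments by weight group possible would be 20 versus 8 patients in the third portion".

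The core-phase dose is fixed from baseline weight (Protocol 6.1.1). In Appendix B.1 the last Regimen 2 row, from 63 kg upward, begins "1.1 (cap injection volume" and corresponds to 192.5 mg. For Regimens 1 and 3 the last row starts at 72.5 kg and gives 148.75 mg.

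Protocol 11.4.4 pools all available PK data and summarises troughs by dose, overall and by weight group. Model-predicted exposure "following the first dose will be summarized using descriptive statistics by dose and weight group". PD follows the same layout (Protocol 11.4.4, SAP 2.4.9). For efficacy, SAP 2.4.6 states: "Efficacy analyses will be done by dose regimen cohort and by weight group". SAP 2.4.6.1 then rules out further efficacy subgroups. The SAP's baseline weight classes are below 30 kg and 30 kg or more (SAP 2.1.1).

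**The concern.** A reader of the final report will see Group A columns for two or three regimens next to each other under one label. For the non-selected regimens the label means 30-60 kg. For the selected regimen it means 30 kg and above. A difference between columns in trough, Cmax, AUC, biomarkers or ACR response may then partly reflect body weight and a change from weight-based to fixed dosing. Protocol 4.3.1 itself reports that weight affected sarilumab exposure in adults.

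The primary objective is to describe PK in order to identify a dose for ages 2 to 17. Patients above 60 kg enter only after selection, so these are the first tables that could show how they fare. The third portion has no PK sampling between Baseline and Week 2, so any early concentration data above 60 kg come from the second portion alone.

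**Working it through.** **Inputs.** Group A limits: Protocol 7.2.1 and 8.4. Counts: Protocol 6.1 and 8.4. Caps: Protocol 6.1.1. Volumes: Appendix B.1, at 175 mg/mL. The documents give no weight distribution.

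**1. The plan's own counts.** Selected regimen per weight group: 6 + 12 = 18, as stated. Third-portion cap: 0.70 × 28 = 19.6, rounded to 20, leaving 28 − 20 = 8, as stated. Both reproduce.

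**2. Share of selected-regimen Group A enrolled with no upper weight limit.**
- After the second portion: 12/18 = 67%.
- With 8 third-portion patients: (12 + 8)/(18 + 8) = 20/26 = 77%.
- With 20 third-portion patients: (12 + 20)/(18 + 20) = 32/38 = 84%.

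These are upper bounds on the share above 60 kg. They add planned evaluable patients in the first two portions to planned enrolled patients in the third.

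**3. Can a core-phase patient at or below 60 kg be capped?** Nominal dose at 60 kg is 2 × 60 = 120 mg or 3 × 60 = 180 mg, below the caps of 150 and 200 mg. The caps bind nominally at 150/2 = 75 kg and 200/3 = 66.7 kg. Appendix B reaches its last row at 72.5 kg and 63 kg. So no dose-finding patient can be on a capped core-phase dose, and capped patients can sit only in the selected-regimen column.

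**4. Dose per kg from Appendix B** (volume × 175 / weight).

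| Weight | Regimen 2 | Regimens 1 and 3 |
|---|---|---|
| 30-60 kg (range, 0.1 kg steps) | 2.83-3.11 | 1.86-2.12 |
| 75 kg | 192.5/75 = 2.57 | 148.75/75 = 1.98 |
| 80 kg | 192.5/80 = 2.41 | 148.75/80 = 1.86 |
| 100 kg | 192.5/100 = 1.93 | 148.75/100 = 1.49 |

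Under Regimens 1 and 3, a patient of 80 kg is still at the low end of the 30-60 kg range. Under Regimen 2, a patient of 75 kg is already below it.

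**5. Effect on the column mean, Regimen 2, by assumption.** If k of n patients are capped and weigh 80 kg, and the rest receive 3 mg/kg, the mean is [3(n − k) + 2.41k]/n.
- n = 18: k = 3 gives 2.90 (−3.3%); k = 6 gives 2.80 (−6.6%); k = 12, the maximum, gives 2.60 (−13.2%).
- n = 38: k = 4 gives 2.94 (−2.1%); k = 8 gives 2.88 (−4.2%); k = 16 gives 2.75 (−8.3%).

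The documents do not name the selected regimen. The third-portion flow chart shows every-other-week dosing, and an intermediate regimen is allowed, so Regimen 2 is illustrative.

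**The case against.** A reader might infer that the regimens are not compared like with like when the dose is chosen. The documents do not support that. Protocol 6.1.2.4 and 11.5 base selection on the dose-finding portion, where every Group A patient is at or below 60 kg. Later tables are descriptive and no hypothesis is tested.

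A reader might also infer that heavier patients are hidden and that exposure under the cap goes unexamined. That is too strong as well. The primary analysis in the protocol summary estimates the effect of weight on PK parameters by population modelling. Baseline weight is summarised as a continuous variable, with its maximum, by cohort and weight group. Exposure tables cover actual dose, and individual PK and efficacy plots may be produced. What stands is narrower. The model results may be reported outside the clinical study report (Protocol 11.4.4), the individual concentration listing in SAP 2.4.4 names neither weight nor dose, and nothing comparable to the weight model is visible for ACR.

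Dose per kg is not exposure. The design gives lighter children more mg/kg to reach the same adult target. Against that adult reference, 192.5 mg is 3.75% below 200 mg (192.5/200 = 0.9625), and 148.75 mg is 0.8% below 150 mg. This objection stands, so no exposure shortfall is claimed.

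Parts of the PK text and of the SAP are redacted, and the mock-up tables of SAP Appendix C are not in the text supplied. A split at 60 kg given there cannot be excluded. Finally, the asymmetry is exact only for the core phase: in the extension, a patient on a non-selected regimen can grow past 60 kg before switching.

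**Conclusion.** The point holds for the interim and final core-phase tables produced after selection. Group A has a different weight range in the selected-regimen column than in the others. Capped-dose patients can appear only in that column, and the readable text does not show their concentrations, biomarkers or ACR response separately. The gap matters most for ACR, where no weight analysis is visible; for PK the population model partly covers it.

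The size is unknown, because it depends on how many second- and third-portion patients exceed 60 kg, and in particular 63 or 72.5 kg. Eligibility permits such patients but does not ensure them. The 2% to 13% falls in mean mg/kg rest on an assumed number capped, an assumed weight of 80 kg and Regimen 2; they describe dose only. The regimen choice is not called into question.

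**What to change.** In Protocol 11.4.2 and 11.4.4 and SAP 2.4.4, 2.4.6 and 2.4.9, keep the pooled Group A column at the selected regimen and add two columns by baseline weight: 30-60 kg and above 60 kg. In Group A tables that set regimens side by side, use patients at or below 60 kg at baseline. A footnote giving the number on the capped volume would help, because the cap starts at 63 or 72.5 kg and not at 60 kg.

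The change uses data already collected. It costs extra columns, and the stratum above 60 kg will probably be small, so its summaries should be read as descriptive only. No dosing change is implied.
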